5.4.2.6 Change in Tumor Size in Injected Lesions

For subjects with solid tumors based on modified RECIST 1.1 and iRECIST (if appropriate) assessments, a waterfall plot will be presented for the maximum percent change from baseline

in injected lesions. If a subject has multiple lesions injected, the first injected lesion will be included.

5.5 Pharmacokinetic, Pharmacodynamic, Pharmacogenomic, and Other Biomarker Analyses

5.5.1 Pharmacokinetic Analyses

Plasma concentrations of E7766 will be tabulated and summarized by dose level, day, and protocol specified time. Urine and fecal recovery of E7766 will be tabulated and summarized by dose level, day, and protocol specified collection interval.

The Safety Analysis Set will be used for individual plasma concentration listings. The Pharmacokinetic Analysis Set will be used for all other analyses such as the summaries of plasma concentrations.

E7766 PK parameters will be derived from plasma concentrations by noncompartmental analysis using actual times. Minimally, the following PK parameters will be calculated:

- C_{max} - Maximum drug concentration;
- t_{max} - Time to reach C_{max} following drug administration;
- AUC - Area under the concentration-time curve;
- $t^{1/2}$ - apparent terminal half-life (if data permit);
- CL/F - Apparent total body clearance;
- Vd/F - Apparent volume of distribution;
- R - Accumulation ratio post multiple doses;
- fe - fraction of administered drug excreted/recovered in urine and feces.

Details of the PK analyses will be described in a separate analysis plan and the results will be presented in a separate report. Metabolite PK will also be summarized in this report if exploratory characterization/identification of metabolites in urine and plasma is attempted depending on emerging nonclinical data.

Any exploratory population PK or PK/PD modeling and simulation work, if done, will be described in details in a separate plan and a separate report.

These plans and reports, if done, will be referenced and the high-level results and conclusions will be summarized in the clinical study report.

5.5.2 Pharmacodynamic, Pharmacogenomic, and Other Biomarker Analyses

The effect of E7766 treatment on blood and/or tissue biomarkers, and/or immune cell subsets will be summarized using descriptive statistics. Pharmacodynamic, pharmacogenomic, and other biomarker analyses will be performed and reported separately.

Details of these analyses will be described in a separate analysis plan and reported separately.

5.6 Safety/Tolerability Analyses

Evaluation of DLTs will be performed on the DLT Analysis Set. The number and percentage of subjects with DLT will be calculated.

All safety analyses will be performed on the Safety Analysis Set. Safety data will be summarized on an “as treated” basis using descriptive statistics.

Safety variables include treatment-emergent AEs (TEAEs), clinical laboratory parameters, vital signs, 12-lead electrocardiogram (ECG), ECOG performance status, echocardiogram/MUGA results including left ventricular ejection fraction (LVEF).

Study Day 1 for all safety analyses will be defined as the date of the first dose of study drug.

5.6.1 Extent of Exposure

The duration of treatment, number of study drug administered, and number of subjects requiring dose reductions and dose omission will be summarized.

5.6.1.1 Extent of Exposure to Study Drug

The total number of treatment cycles for each subject is the largest cycle number in which a subject receives any non-zero dose of study drug.

The treatment duration (days) will be calculated as the minimum of (day 1 of the last cycle with non-zero dose+21 days, or treatment disposition date) – date of the first non-zero dose.

5.6.1.2 Study Drug Administered

The total number of dose administrations and total cumulative dose (μ g) received per subject, and relative dose intensity will be summarized with descriptive statistics.

The total number of doses received per subject will be calculated as the total number of injections with non-zero doses administered during the study per subject. The total cumulative dose per subject (μ g) will be calculated as the sum of all doses (μ g) that subject has actually received during the study. The relative dose intensity, which is defined as the ratio (%) of total

dose received and total planned dose (i.e., received dose as a percentage of sum of planned doses), will be calculated.

Number of injected lesions per subject will also be summarized.

5.6.1.3 Study Drug Dose Modifications

The guidance of E7766 dose modifications for Dose Escalation part and Dose Expansion part are outlined in protocol.

Dose reduction refers to a situation that a planned dose level was reduced from the previous dose level without going back the previous dose level. Dose omission only refers to the scenario that the dose levels before and after omission period (defined as the period with planned dose=0) are the same. If the subject discontinued from treatment permanently after dose omission with planned dose=0, it should be counted as treatment discontinuation instead of dose omission.

The number of subjects with dose reductions and dose omission will be summarized.

Subject data listings will be provided for all dosing records.

5.6.2 Adverse Events

5.6.2.1 Dose Limiting Toxicity

The number and percentage of subjects with DLT will be summarized for DLT Analysis Set.

Subject data listing will be provided for DLT records.

5.6.2.2 Adverse Events

The AE verbatim descriptions (investigator terms from the CRF) will be classified into standardized medical terminology using the Medical Dictionary for Regulatory Activities (MedDRA). Adverse events will be coded to the MedDRA (Version 21.1 or higher) lower level term (LLT) closest to the verbatim term. The linked MedDRA preferred term (PT) and primary system organ class (SOC) are also captured in the database.

A TEAE is defined as an AE that emerges during treatment (on or after the first dose of study drug up to 90 days after the subject's last dose) or start day of another anticancer therapy, whichever is earlier; or in case subject has initiated new anticancer therapy within 30 days, the AEs occurring for 30 days following the last dose of study drug, having been absent at pretreatment (baseline) or

- Reemerges during treatment, having been present at pretreatment (baseline) but stopped before treatment, or

- Worsens in severity during treatment relative to the pretreatment state, when the AE is continuous, or

Only those AEs that are treatment-emergent will be included in summary tables. All AEs, treatment-emergent or otherwise, will be presented in subject data listings.

Overview of TEAEs

An overview of TEAEs reported through the study will be provided. Overall summary of TEAE will include the number and percentage of subjects with TEAEs, serious TEAEs, TEAEs of Grade 3 or higher, TEAEs leading to treatment discontinuation, TEAEs leading to dose reductions, TEAEs leading to dose interruptions, and TEAEs with fatal outcomes. Similar summaries for treatment-related TEAEs will also be provided.

All TEAEs

All TEAEs will be summarized by SOC and PT. A subject will be counted only once within an SOC and PT, even if the subject experienced more than 1 TEAE within a specific SOC and PT. The TEAEs will also be summarized by SOC, PT, and worst Common Terminology Criteria for Adverse Events (CTCAE) grade.

Treatment-related TEAEs

Treatment-related TEAEs will be summarized by SOC and PT. Treatment-related TEAEs include those events considered by the investigator to be related to study drug. Treatment-related TEAEs will also be summarized by SOC, PT, and worst CTCAE grade.

Grade 3 or higher TEAEs

The grade 3 or higher TEAEs will be summarized by SOC and PT. A subject data listing of grade 3 or higher AEs will be provided.

Serious TEAEs

Serious TEAEs will be summarized by SOC and PT. Similar summary for treatment-related serious TEAEs may also be presented. A subject data listing of all SAEs will be provided.

TEAEs Leading to Treatment Discontinuation

The TEAEs leading to discontinuation from study drug will be summarized by SOC and PT. A subject data listing of all AEs leading to discontinuation from study drug will be provided.

TEAEs Leading to Dose Reductions and Dose Interruptions

The TEAEs leading to dose reductions and/or dose interruptions will be summarized by SOC and PT. A subject data listing of AEs leading to dose reductions and/or dose interruptions of study drug will be provided.

TEAEs with Fatal Outcome

The TEAEs with fatal outcome will be summarized by SOC and PT. Similar summary for treatment-related TEAEs with fatal outcome may also be presented.

A subject data listing of AEs with fatal outcome will be provided. A listing of the AEs with fatal outcome not due to PD may also be provided.

Deaths

The number of subjects who died during the study will be summarized. In addition, the number of deaths within 90 days of last dose will also be presented.

A listing of subjects who died during the study will be provided.

5.6.3 Laboratory Values

Clinical laboratory tests to be performed for this study, including hematology, chemistry, and urinalysis.

Laboratory results will be summarized using standard units, as appropriate.

Laboratory parameters will be graded according to CTCAE Version 5.0. In the summary of laboratory parameters by CTCAE grade, for parameters with CTCAE grading in both high and low direction (eg, calcium, glucose, magnesium, potassium, sodium), CTCAE grades in both high and low directions will be summarized separately.

Descriptive statistics for values and changes from baseline at each scheduled visit for quantitative hematology and chemistry laboratory parameters will be provided. Boxplots of laboratory values over time may be provided for selected hematology and chemistry parameters for subjects in the expansion cohort.

In selected hematology and chemistry parameters, the worst CTCAE grade postbaseline and shift from baseline will be summarized in shift tables. Subject with nonmissing baseline and postbaseline results will be used as denominators in shift tables.

Calcium corrected for albumin (mmol/L) will be calculated as:

Calcium measured (mmol/L) + 0.025 (40 - Albumin (g/L)).

if result for Albumin is > 40 g/L, then calcium corrected for albumin (mmol/L) = Calcium measured (mmol/L).

if albumin was missing, then calcium corrected for albumin is missing

5.6.4 Vital Signs

Descriptive statistics for vital sign parameters (ie, systolic and diastolic blood pressure, pulse, respiratory rate, temperature, weight) and changes from baseline will be presented by visit.

A subject data listing of vital signs will be provided.

5.6.5 Electrocardiograms

ECG data includes 24 hour continuous Holter ECG, central and local 12-lead ECG data.

Only local ECG data will be used for safety analysis. Descriptive statistics for ECG parameters and changes from baseline will be presented by visit. Shift tables will be presented for the changes from baseline in ECG interpretation (categorized as normal; abnormal, not clinically significant; and abnormal, clinically significant) to worst postbaseline category.

In addition, the number (percentage) of subjects with at least 1 postbaseline abnormal ECG result in QTc Fridericia (QTcF) postbaseline will be summarized. Clinically abnormal ECG results in QTcF will be categorized as follows:

Absolute QTcF interval prolongation:

- QTcF interval >450 ms
- QTcF interval >480 ms
- QTcF interval >500 ms

Change from baseline in QTcF interval:

- QTcF interval increases from baseline >30 ms
- QTcF interval increases from baseline >60 ms

A subject data listing of local ECG only will also be provided.

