#### **Safety Assessments**

Safety assessments will consist of monitoring and recording all AEs, including all CTCAE 5.0 AEs (for both increasing and decreasing severity), and serious adverse events (SAEs); regular laboratory evaluation for hematology, blood chemistry, and urine values; and periodic measurement of vital signs, echocardiograms/MUGA scans, safety ECGs, and physical examinations.

Additionally, QTc intervals will be evaluated in the Dose Escalation part only, unless a signal indicates the need for continued monitoring in the Dose Expansion part. The effects of E7766 on cardiac repolarization will be evaluated via 24-hour, 12-lead continuous Holter/ECG monitoring during Baseline, Cycle 1 Day 1, Cycle 1 Day 14, and Cycle 1 Day 15 of the Dose Escalation part of the study only. Replicate 12-lead ECGs will be extracted from the Holter recordings at specified time points and will be evaluated by a central laboratory. QT intervals will be measured from Lead II and will be corrected for QTc using Fridericia's correction factor (QTcF). The primary QTc parameter will be QTcF. Secondary parameters (heart rate, PR interval and QRS) and treatment emergent T wave abnormalities and U-waves will be evaluated. Potential effects of E7766 will be evaluated as change-from predose baseline heart rate, PR interval, QRS and QTcF by postdosing time point. For purposes of QT assessment, exposure response analysis will be performed of the relationship between E7766 plasma levels and  $\Delta$ QTcF.

In preclinical studies, intratumorally or subcutaneously administered E7766 upregulated expression of certain cytokines in the blood suggesting a possibility of inducing CRS in patients who will receive E7766 treatment. In case a CRS-like symptom occurs, tocilizumab (anti-IL6R) and standard practice by clinical sites may be given to the subjects according to the "Management of Cytokine Release Storm and Organ Toxicity" table shown above.

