### 9.5.1.5.6 ELECTROCARDIOGRAMS

Electrocardiograms will be obtained as designated in the Schedule of Procedures /Assessments (Table 7). Complete, standardized, 12-lead ECG recordings that permit all 12 leads to be displayed on a single page with an accompanying lead II rhythm strip below the customary 3 × 4 lead format are to be used. In addition to a rhythm strip, a minimum of 3 full complexes should be recorded from each lead simultaneously. Subjects must be in the recumbent position for a period of 5 minutes prior to the ECG.

An ECG abnormality may meet the criteria of an AE as described in this protocol (see Section 9.5.1.5.1) and the CRF Completion Guidelines. In these instances, the AE corresponding to the ECG abnormality will be recorded on the Adverse Event CRF.

Additionally, QTc intervals will be evaluated in the Dose Escalation part only, unless a signal indicates the need for continued monitoring in the Dose Expansion part.

The effects of E7766 on cardiac repolarization will be evaluated via 24-hour, 12-lead continuous Holter/ECG monitoring during Baseline, Cycle 1 Day 1, Cycle 1 Day 14, and Cycle 1 Day 15 in the Dose Escalation part of the study only. Additionally, cardiodynamic evaluation, including concentration-QTc (C-QTc) analysis will be performed in the Dose Escalation part only, unless a signal indicates the need for continued monitoring in the Dose Expansion part. For this purpose, replicate 12-lead ECGs will be extracted from 24-hour

Eisai Confidential Page 86 of 138

continuous recordings (Holters) by a central ECG laboratory at time points, as detailed in the Schedule of Procedures/Assessments (Table 7). QT intervals will be measured from Lead II and will be corrected for QTc using Fridericia's correction factors (QTcF). The primary QTc parameter will be QTcF. Secondary parameters (heart rate, PR interval and QRS) and treatment-emergent T wave abnormalities and U-waves will be evaluated. Potential effects of E7766 will be evaluated as change-from predose baseline heart rate, PR interval, QRS, and QTcF by postdosing time point. For purposes of QT assessment, concentration-QTc analysis will be performed of the relationship between E7766 plasma levels and ΔQTcF.

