- c. In the Dose Escalation part, subjects will be admitted at Baseline and on Cycle 1 Day 14 to the study clinic. In the Dose Escalation part, on Day 1 of Cycle 1 (ie, after the first dose only), subjects will remain at the study clinic for at least 30 hours after E7766 administration for monitoring of safety and can be discharged on Cycle 1 Day 2 if there are no safety concerns.
- d. A comprehensive physical examination will be performed at Screening and at the Off-Treatment Visit. A symptom-directed physical examination will be performed on Day 1 of all treatment cycles and at any time during the study, as clinically indicated. Vital signs include BP, HR, RR, and body temperature, as well as weight and height. BP, HR, and RR will be collected after the subject has been sitting for 5 minutes. Height will be measured at the Screening Visit only. On all dosing days, vital signs should be measured prior to dosing. On Day 1 of Cycle 1, vital signs should be obtained postdose within 2 hours of dosing, and subsequently every 4 hours or as clinically indicated for 30 hours postdose. On the other dosing days, vital signs should be assessed postdose within 2 hours of dosing. Vital signs will also be assessed at the Off-Treatment Visit.
- e. Echocardiograms or MUGA will be performed at Screening, during the Off-Treatment Visit (window of ±1 week), and if clinically indicated. MUGA scans and echocardiograms will be performed locally in accordance with the institution's standard practice.
- f. A serum pregnancy test (β-hCG) will be performed at Screening for all premenopausal women and postmenopausal women who have been amenorrheic for less than 12 months. A urine or serum pregnancy test will be performed at Baseline, before the first dose of E7766 on Cycle 1 Day 1, on Day 1 of all subsequent cycles before E7766 dosing, and at the Off-Treatment Visit.
- g. 12-Lead ECGs will be collected locally at the following time points: Screening (single) and Baseline (single unless abnormalities are observed or if clinically indicated, then in triplicate at 2-minute intervals); Day 1 of all Cycles (before and after [within 1 to 2 hours after E7766 injection]); and at Off-Treatment Visit. In case of any alteration, or if clinically necessary, an echocardiogram and/or cardiac enzymes should be performed.

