5.7 Other Analyses

No other analysis is planned.

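### The SAP confines ECG safety analysis to local readings and does not plan, refer elsewhere by name, or declare removed the protocol's central Holter QTcF and concentration-QTc analyses

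*SAP*

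**What the plan says.** Protocol 9.5.1.5.6 has a central laboratory extract replicate ECGs from 24-hour Holter recordings in Dose Escalation, with QTcF as the primary QTc parameter. It then says how they are to be used: "Potential effects of E7766 will be evaluated as change-from predose baseline heart rate, PR interval, QRS, and QTcF by postdosing time point". It adds that "cardiodynamic evaluation, including concentration-QTc (C-QTc) analysis will be performed in the Dose Escalation part only", unless a signal calls for more monitoring in expansion. The synopsis, under Safety Assessments, makes the same commitment: "For purposes of QT assessment, exposure response analysis will be performed of the relationship between E7766 plasma levels and" change in QTcF.

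SAP 5.6.5 acknowledges all the sources: "ECG data includes 24 hour continuous Holter ECG, central and local 12-lead ECG data". It then states "Only local ECG data will be used for safety analysis", and for the listing, "A subject data listing of local ECG only will also be provided". By-visit summaries, the interpretation shift table and the QTcF category counts (>450, >480 and >500 ms; increases >30 and >60 ms) follow from that source. Concentration-QTc does not appear in the SAP. Section 5.7 reads "No other analysis is planned". Section 7 lists six removals for the abbreviated CSR, among them ECOG and MUGA/echocardiogram; Holter, central ECG and concentration-QTc are not on that list.

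**The concern.** The protocol describes these analyses as ones that will be done, and the SAP's ECG rule departs from that without explanation. Section 7 is where such a departure should be declared, and other safety analyses were declared there.

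The source of the readings matters because of what is left to report. Expansion was cancelled (SAP 3.2.2), the MTD was not determined and the MUGA/echocardiogram analysis is removed (SAP 7). Safety and tolerability is then the main primary objective still reportable, and the local ECG tables are the main cardiac analysis still planned. Few local readings fall on Cycle 1 dosing days, when injections are weekly. A clean QTcF table built on them could be taken as more reassurance than the schedule can give, in a study that is first-in-human for this route.

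**Working it through.** No sample size, power or alpha enters here. The check is a count of scheduled time points from Protocol Table 7 and its footnotes, followed by a search of the SAP for a home for the missing analyses.

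**Inputs**
- Central (footnote h): post-dose extractions at end of administration and at 0.25, 0.5, 1, 1.5, 2, 3, 4, 5, 6, 8, 10, 12 and 24 h, on Days 1 and 15 of Cycle 1.
- PK (footnote k, Dose Escalation): post-dose samples at 0.25, 0.5, 1, 1.5, 2, 3, 4, 6, 8, 10, 12 and 24 h on the same two days.
- Local (footnote g and Table 7): Screening, Baseline, "Day 1 of all Cycles (before and after [within 1 to 2 hours after E7766 injection"]), and Off-Treatment. Table 7 marks no local ECG on Cycle 1 Days 2, 8, 14, 15 or 16.
- SAP 8.2: the pre-dose ECG on the first dosing day is the baseline.

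**Central post-dose points in Cycle 1**
- Per dosing day: 1 (end of administration) + 13 timed = 14.
- Two days: 14 × 2 = 28.
- Matched by nominal time to a PK sample: 12 per day (the 5 h and end-of-administration points have none), so 12 × 2 = 24 available for a concentration-QTc model.

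**Local post-dose ECGs in Cycle 1**
- Day 1 at 1 to 2 h: 1. Day 8: 0. Day 15: 0. Total: 1.
- Of the 13 timed Holter points per day, 1, 1.5 and 2 h fall inside the local window. The other 10 (0.25, 0.5, 3, 4, 5, 6, 8, 10, 12 and 24 h) do not.

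**Local post-baseline ECGs over the whole study**
- For a subject treated in k cycles: k post-dose readings + (k − 1) pre-dose readings in later cycles + 1 Off-Treatment = 2k scheduled.
- k = 1 gives 2; k = 6 gives 12. Unscheduled ECGs come on top.
- The only scheduled local reading after an injection in Cycle 1 remains the single one on Day 1.

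**Where else the analyses might sit**
- SAP 5.5.1 puts PK details in a separate plan, and population PK or PK/PD modelling in another if it is done. SAP 5.5.2 does the same for biomarkers. None of these names central ECG or concentration-QTc.
- Protocol 9.7.1.8.5 specifies by-visit summaries, shift tables and the same QTcF categories, and does not say whether local or central readings feed them.

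**The case against.** Several stronger readings are tempting, and the documents do not support them.

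- **That the central data are dropped silently.** SAP 5.6.5 states the local-only rule openly, twice. What is missing is the reason, any mention of concentration-QTc, and a Section 7 entry.
- **That QT safety is judged on a single post-dose ECG.** That count holds for Cycle 1 only. The category table counts subjects with any abnormal post-baseline result, and even a one-cycle subject has two scheduled post-baseline local readings.
- **That prolongation outside 1 to 2 hours cannot appear in the tables.** Later pre-dose and Off-Treatment ECGs lie outside that window. SAP 8.1 brings unscheduled assessments into shift tables. Protocol 9.5.1.5.1 treats QTcF above 450 ms with a rise of more than 60 ms as an AE, without restricting the ECG source, so such an event could reach the TEAE tables.
- **That the central data will go unused.** The SAP restricts safety analysis, not every use. A separate PK plan exists by reference and might include concentration-QTc. SAP 5.7 proves little, because the same SAP sends other analyses to separate reports.
- **That central readings must replace local ones in the category table.** Protocol 9.7.1.8.5 does not require it.

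It can also be said that early termination and an abbreviated CSR make reduced ECG reporting a reasonable choice. That may be so, but it would then be a change in planned analysis, and Section 7 does not record it. These points narrow the concern. They leave the mismatch between the protocol's commitment and the SAP in place.

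**Conclusion.** The concern holds in limited form. The protocol commits Dose Escalation to central Holter QTcF by time point and to a concentration-QTc analysis. The SAP adopts a different ECG source, gives no reason, and does not plan those analyses, point to them by name, or declare them removed. This is a stated rule that departs from the protocol, so it is more than missing detail.

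In Cycle 1 the gap is 28 scheduled central post-dose points (24 matched to PK) against one local post-dose ECG, with the Day 8 and Day 15 injections having no scheduled local ECG. A prolongation on a Cycle 1 dosing day away from the Day 1 reading would probably, though not certainly, be missed by the QTcF tables.

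The counts assume that visits and recordings follow Table 7. The conclusion about missing analyses rests on the two documents alone; a cardiodynamic plan that neither of them cites would change the remedy to a cross-reference.

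**What to change.** In SAP 5.6.5, add for Dose Escalation (a) central Holter QTcF change from predose baseline by post-dose time point, together with heart rate, PR and QRS as the protocol specifies, and (b) the concentration-QTc analysis. Report the QTcF categories from the central readings alongside the local-ECG table, which stays.

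If a separate plan already covers these analyses, cite it in 5.6.5. If they are being dropped, say so in Section 7 with the reason. Either of these costs a sentence or two.

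The full addition costs a few tables and one model. That estimate assumes the Holter extractions and central readings are complete. SAP 5.6.5 lists central data as part of the study's ECG data, but neither document confirms that the reading has been finished.
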